14.4 Analysis Conventions

14.4.1 Analysis Sets

Full Analysis Set: The Full Analysis Set (FAS) will consist of all subjects who are enrolled in the study.

Injection Analysis Set: The Injection Analysis Set will include all patients who undergo a successful NKA injection.

14.4.2 Handling Missing Data

Values for missing data will not be imputed.

14.5 Demographic and Baseline Characteristics

Demographic data and baseline characteristics will be summarized using a typical 8-number summary (sample size, mean, standard deviation, median, Q1, Q3, minimum, and maximum) for continuous variables and frequency and proportion for categorical variables. These summaries will be produced for both the FAS and the Injection analysis set. Generating inferential statistics is not planned. Demographic and baseline characteristics information will be provided in a data listing.

14.6 Efficacy Analysis

Not applicable.

14.7 Safety Analysis

14.7.1 Biopsy, NKA Injection, Patient Disposition

Biopsy and NKA injection data will be provided in a data listing. Patient disposition (e.g., Screen Failure, Enrolled/Underwent Injection, Withdrawn Pre-injection, Successful injection, Discontinued Early Post-injection, Completed Study) will be summarized by frequency and proportion and will be provided in a data listing.

14.7.2 Adverse Events

Clinical and laboratory AE's will be coded using the Medical Dictionary for Regulatory Activities (MedDRA). System Organ Class (SOC), High-Level Group Term (HLGT), High-Level Term (HLT), Preferred Term (PT), and Lower Level Term (LLT) will be attached to the clinical database. Adverse events will be graded using the NCI CTCAE scale.

A treatment-emergent AE will be defined as any adverse event that begins on or after the date of enrollment up to 18 months post-injection.

Summaries (frequency and proportion) of treatment-emergent AE's will be presented by SOC and PT.

Additional summaries will include, but are not limited to, treatment-emergent AE's by severity grade, Investigator's assessment of relationship to procedure and/or product, serious AE's (SAE's), related SAE's, and deaths. AE summaries will be provided for both the FAS and the Injection analysis set. There are no plans to generate inferential statistics. AE data will be provided in a data listing.

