- 22. Patients with bleeding disorders that would, in the opinion of the Investigator, interfere with the performance of study procedures; patients taking coumarins (e.g. Warfarin) or other anticoagulants (e.g. enoxaparin or direct thrombin inhibitors).
- 23. Any circumstance in which the investigator deems participation in the study is not in the subject's best interest.
- 24. Use of any investigational product within 3 months of the injection without receiving prior written consent of the Medical Monitor.

Number of Sites: Up to 10 clinical centers will be included in the study.

Study Duration: 18 months NKA injections follow up followed by 24 month long term follow up for a total study duration of 42 months.

Study Enrollment: Up to 30 subjects undergoing NKA injection will be enrolled into the study. Patients who have received a single injection of NKA under previous research protocols may enroll in this clinical trial to receive a single additional injection. Patients who have never received an NKA injection may enroll in this clinical trial for up to a total of two (2) NKA injections, temporally spaced at least 6 months apart. All biopsies are to be taken from a single kidney, and all NKA injections are to be given into the kidney that was biopsied. Patients who complete screening procedures satisfying all I/E criteria will be enrolled into the study immediately prior to the injection. Patients who do not meet all criteria before injection will be considered screen failures. Once a patient has been injected, the patient will have completed treatment and every effort should be made to ensure the patient completes all follow-up visits. Injection dates for the first 3 patients receiving their second NKA injection will be staggered by a minimum of 3 week intervals to allow for assessment of acute adverse events and other safety parameters by the DSMB. Subsequent second injections will continue to be staggered so as to occur no less than 3 weeks apart, but individual DMSB review will not be required. At the completion of the follow-up visits, patients will continue in a long-term follow-up study. Patients will be followed for a total of 36 months following the last NKA injection under this protocol, whether the first or second injection.

Investigational Plan:

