10 STUDY POPULATION

10.1 Eligibility Criteria

Eligibility criteria should be assessed at Screening. In addition, unless otherwise noted for the specific criterion, eligibility criteria should be also be reviewed before the biopsy and at the Day -10 to -14 pre-injection visit.

Up to 30 subjects will be enrolled in this study, including subjects previously injected in either Phase 1 trial. Note that a subject will be considered enrolled into the study at the time of injection.

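### No planned summary gives a procedure-related AE rate over all biopsied patients: those never injected are in neither AE analysis set, and AEs between biopsy and injection are not treatment-emergent

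*Combined protocol and SAP*

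**What the plan says.** **Time of enrollment.** Section 10.1 says: "Note that a subject will be considered enrolled into the study at the time of injection". The synopsis (Study Enrollment) says that patients who pass screening "will be enrolled into the study immediately prior to the injection". Section 10.3 agrees: a patient who withdraws after biopsy and before injection does not count as enrolled and can be replaced. Section 11.2 places the biopsy 4 to 14 weeks before injection.

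**Analysis sets (14.4.1).** "The Full Analysis Set (FAS) will consist of all subjects who are enrolled in the study". "The Injection Analysis Set will include all patients who undergo a successful NKA injection".

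**AE summaries (14.7.2).** The treatment-emergent window is defined as: "A treatment-emergent AE will be defined as any adverse event that begins on or after the date of enrollment up to 18 months post-injection". The SOC/PT table is of treatment-emergent AEs. The further summaries are open-ended: "Additional summaries will include, but are not limited to, treatment-emergent AE's by severity grade", followed by relationship, SAEs, related SAEs and deaths. On the sets: "AE summaries will be provided for both the FAS and the Injection analysis set". AE data are also listed.

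**Primary safety outcome (14.3).** This is procedure- and/or product-related AEs. It ends 12 months after the first injection and has no stated start. Section 13.3.3 gives biopsy as an example of a study procedure.

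**Stopping between biopsy and injection.** Sections 9 and 12.5.1 have patients discontinued when the PI judges that significant biopsy AEs make injection unsafe or too risky. Section 13.4.1 asks the PI to consider it when an AV fistula is found at the pre-injection visit.

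**The concern.** New patients must have the biopsy, because it supplies the cells for NKA. Its harms belong in any account of what the treatment involves, and the protocol treats them that way by naming pain, hemorrhage and AV fistula after biopsy as events of special interest (13.4.1).

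Both analysis sets begin at injection. A patient whose biopsy complication prevents injection therefore leaves the numerator and the denominator together, and leaves because of the outcome being measured. A replacement who got through the biopsy can then take the place. A procedure-related AE proportion built this way can only be too low with respect to these patients. Describing safety is the stated purpose of the sample size (14.1), so this affects one of the study's main outputs.

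**Working it through.** There is no planned figure to reproduce, since no sample size calculation was done. The check traces the definitions and then illustrates the size.

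**Step 1: biopsied, never injected.** Such a patient is not enrolled (10.1, 10.3), so is not in the Full Analysis Set. The patient had no successful injection, so is not in the Injection Analysis Set. AE summaries are assigned to those two sets only (14.7.2), so the patient is in no AE summary. This follows directly from the text.

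**Step 2: biopsied, later injected, with an AE that starts before injection.** The patient is in the sets. The AE starts before the date of enrollment, so it is not treatment-emergent and is outside the SOC/PT and severity tables. The relationship, SAE, related-SAE and death summaries are not clearly limited to treatment-emergent AEs and might include it. This gap is partial.

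**Step 3: what remains.** Biopsy-related AEs and all SAEs go on the CRF (13.3.1, 13.3.2). AE data are listed (14.7.2), biopsy data are listed, and disposition is tabulated (14.7.1). None of these is an AE rate over biopsied patients. The disposition count is also not a clean denominator. The synopsis says "Patients who do not meet all criteria before injection will be considered screen failures", whereas 10.3 says that a patient who withdraws after biopsy is not a screen failure. A biopsied patient stopped before injection could be put in either category.

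**Step 4: illustration of size.** Inputs:
- At most 30 patients injected, including returning Phase 1 patients (10.3).
- 7 Phase 1 patients (section 6). If all return and their frozen cells suffice, newly biopsied injected patients number 30 − 7 = 23.
- k = patients stopped for biopsy harm, assumed 1 to 3. The documents give no figure.

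With no other attrition, the rate of such stops among biopsied patients is k / (biopsied and injected + k):

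| k | 30 injected, all biopsied here | 23 biopsied, 7 not | Shown in planned sets |
|---|---|---|---|
| 1 | 1/31 = 3.2% | 1/24 = 4.2% | 0 |
| 2 | 2/32 = 6.2% | 2/25 = 8.0% | 0 |
| 3 | 3/33 = 9.1% | 3/26 = 11.5% | 0 |

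Patients lost for other reasons (unusable tissue, lost eligibility, choice) enlarge the denominator. At an assumed 20% total attrition, 30 / (1 − 0.20) = 37.5, rounded up to 38 biopsied. Three stops for harm are then 3/38 = 7.9%.

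These figures count only patients stopped for harm, not all procedure-related AEs.

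**The case against.** The strongest reply is that nothing is hidden. Biopsy-related AEs are on the CRF and in the listing, all events are to be included in the final report (13.1.1), and patients who stop after biopsy have an end-of-study visit (11.4). The synopsis counts events of special interest in the safety profile, and the DSMB reviews unexpected procedure-related events case by case (13.5). With some two or three dozen biopsies, a reader could count the denominator from the biopsy listing. The study is descriptive, with no inferential AE analysis. All of this stands and limits the consequence, but a hand count from listings is not a planned rate.

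On disposition, most stops for biopsy harm would fit the pre-injection withdrawal category under 10.3, so the conflict with the synopsis is secondary.

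A reader might infer more than the documents support:
- **That biopsy harms are absent from the report, or from every summary.** They are recorded and listed, and for injected patients the open-ended summaries might include them.
- **That omission is likely.** Section 13.4.1 cites about 18% AV fistula and about 3% macroscopic hematuria or painful hematoma after biopsy. These are occurrence rates. The share of such patients who would be stopped is not given, and the number of biopsies depends on how many are replaced, so a probability of omission would rest on invented inputs.
- **That Phase 1 settles the matter either way.** Its 7 patients are described as biopsied and injected. A patient stopped after biopsy would not be in that count, so it says nothing about stopping.

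**Conclusion.** The point holds. Under the stated definitions, a biopsied patient who is never injected is in no AE summary. AEs starting between biopsy and injection are outside the SOC/PT and severity tables even in patients later injected. The plan therefore gives no procedure-related AE rate over biopsied patients, although such AEs are the primary safety outcome and biopsy is a named study procedure.

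The bias is conditional. If any patient is stopped for biopsy harm, the rate is too low. In the illustration, 3.2% to 11.5% of biopsied patients would be shown as none, and less if others are lost for other reasons. That range assumes 1 to 3 such stops, 30 injected, and either 0 or 7 returning patients who need no biopsy. If no patient is stopped for biopsy harm, the first gap causes no bias and only the partial second gap remains.

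This should be fixed before analysis. The definitional part is certain, while the size is illustrative only.

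**What to change.** 1. In 14.4.1, add a Biopsy Safety Set: all patients who start a study biopsy under this protocol.
2. In 14.7.2, add one table on that set, showing procedure-related AEs and all SAEs (including deaths) by relationship and severity. It runs from the start of biopsy to the first injection under this protocol, or to the end of follow-up if never injected. Report it as part of the primary safety outcome.
3. Keep the post-injection treatment-emergent tables on the Full Analysis Set and the Injection Analysis Set as planned, so that never-injected patients do not dilute NKA-related rates.
4. Reconcile the synopsis with 10.3 so that biopsied patients stopped before injection have one disposition category.

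**Cost.** One set, one table and some wording. No new data are needed, because 13.3.1 and 13.3.2 already collect these events. The reported procedure-related AE rate may be higher. The biopsy-period denominator will differ from the injection-period one, because returning patients may not need a biopsy.

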6.5.3 Selection of Kidney for Biopsy/Injection

Laparoscopic surgical techniques can be used to access either the right or left kidney. However, the left kidney is more readily accessible and is most often accessed during nephrectomies, hence the first surgical team had more experience with accessing the left kidney, and the initial patients enrolled underwent left kidney biopsy and left kidney NKA injection. Patients previously enrolled may have a second NKA injection in the left kidney. Newly enrolled patients may have either the left or right kidney biopsied. In any case, the NKA injection should be made into the kidney that was biopsied.

6.6Benefit: Risk Assessment

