11.2 Biopsy (4 to 14 Weeks before Injection)

The biopsy should be scheduled within 45 days following the first screening assessment. The biopsy should be scheduled so that the injection procedure can be scheduled at 4 weeks or later. Due to shipping and manufacturing schedules, the preferred days for collecting the biopsy are Wednesday or Thursday. Biopsies should not be collected on a Friday.

Patients should report to the site one to three days before the biopsy for pre-biopsy assessments. As much as possible, pre-biopsy laboratory samples may be collected and assessed to verify patient eligibility prior to biopsy.

Following final review of appropriate eligibility criteria, the biopsy should be performed as described below in Section 12.5.1. The biopsy should be sent to RegenMed (Cayman) Ltd. in the shipping container provided by RegenMed (Cayman) Ltd. according to procedures detailed in the Study Reference Manual. After the biopsy, the patient should remain in the hospital overnight for observation. As long as any biopsy-related AEs have resolved, stabilized, or returned to baseline, the patient may be discharged the same day as biopsy per site standard practice.

Once the biopsy is received at RegenMed (Cayman) Ltd., the biopsy will be assessed and processed according to RegenMed (Cayman) Ltd.'s SOPs for product manufacturing. One to two weeks after receiving the biopsy in North Carolina, RegenMed (Cayman) Ltd. will notify the site concerning the adequacy of the sample for manufacture of NKA. Following the notification to proceed, the site can confirm the injection date. If the biopsy cannot be used for manufacture of NKA, the patient should be discontinued from the study.

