13 SAFETY ASSESSMENTS AND MANAGEMENT

13.1 Event Definitions

13.1.1 Adverse Events

An Adverse Event (AE) is any untoward medical occurrence associated with the use of a drug or with study participation, regardless of the relationship of the occurrence to study drug or protocol. An AE can be any unfavorable and unintended sign (including an abnormal laboratory finding), symptom or disease temporally associated with the use of the drug, whether or not considered related to the drug. An AE can arise from any use of the drug, and from any route of administration, formulation or dose, including an overdose.

Disease or other specific clinical signs and symptoms which were ongoing prior to study entry (i.e., a "pre-existing" conditions) should be recorded on the Medical History CRF and are not considered AE's unless the condition unexpectedly worsens during the study. Specifically, CKD signs and symptoms which were present at study entry and had been worsening over time are not considered AE's unless there is an unexpected worsening of the events. This would include, for example, an unexpected increase in the rate of disease progression.

Treatment emergent abnormal clinical laboratory findings or other abnormal assessments that are judged by the PI as clinically significant, involve therapeutic medical intervention, or lead to study discontinuation will be recorded as AE's or SAE's if they meet the definition of an AE or SAE presented in this section.

To determine the presence of adverse events, patients should be questioned about the event in a general way, without asking about the occurrence of any specific symptom. The investigator should attempt to establish a diagnosis of the event based on signs, symptoms, and/or other clinical information. In such cases the diagnosis should be documented as the AE and not the individual signs and/or symptoms.

Following questioning and evaluation, all AE's, whether believed by the investigator to be related or unrelated to study procedures and/or NKA, must be documented in the patient's medical records in accordance with the investigator's normal clinical practice and on the AE CRF. Each AE is to be evaluated for nature, duration, severity, seriousness, and causal relationship to NKA administration.

All events will be managed and reported in compliance with all applicable regulations, and included in the final study report.

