13.4.1 Procedure-related Events

Post-procedure Pain: If the subject experiences pain following the biopsy or injection, simple analgesia with paracetamol or paracetamol-codeine combinations usually suffices to control the pain. More severe pain in the loin or abdomen requires ultrasonography to exclude significant perirenal hemorrhage. Patients will be followed with regular hemoglobin and blood pressure monitoring. If severe pain occurs, opiates may be necessary. If analgesic doses higher than the maximum authorized doses are required to alleviate pain, then the Investigator must perform additional clinical evaluations to ascertain the probable cause(s) of excessive pain.

Hemorrhage: A degree of perirenal bleeding accompanies almost every renal biopsy. According to the literature (Whittier and Korbet, 2004b), mean hemoglobin decreases approximately 1.0 g/L to about 10 g/L after injection biopsy. Macroscopic hematuria and painful hematomas are seen in about 3 % of patients after renal biopsy. Therefore, following the biopsy and injection, patients will be followed with regular hemoglobin and blood pressure monitoring. Patients will be confined to bed and monitored for maintenance of normal coagulation indices. If bleeding is brisk and the patient is hypotensive despite bed rest, blood transfusion will be considered. If the bleeding is still not controlled, surgery may be considered. In rare cases, renal angiography should be performed to identify the source of bleeding and coil embolization can be performed in such cases during the same procedure. **Arteriovenous (AV) fistula:** According to the literature (Abutaleb and Obaideen, 2007; Arora et al., 2012; Ham et al., 2012; Huang et al., 2011; Whittier and Korbet, 2004a; Whittier and Korbet, 2004b), AV fistulas can be found in about 18% of patients that have undergone renal biopsy. However, as more than 95% of these resolve within 2 years, they should not be routinely pursued. If patients have recurrent hematuria after a renal biopsy or injection, AV fistulas could be considered. In these cases embolization may be indicated. If an AV fistula is detected by ultrasound at the pre-injection qualification visit, then the PI should consider discontinuing the patient prior to injection.

Other complications: In very rare cases other organs, such as liver, gallbladder and lungs may have been penetrated during the procedure. In these cases appropriate treatment and follow-up will be discussed with surgeons.

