14.7.3 Laboratory Evaluations

Baseline values will be collected immediately prior to injection. Observed and change from baseline laboratory data will be summarized using a typical 8-number summary (sample size, mean, standard deviation, median, Q1, Q3, minimum, and maximum) for continuous variables and frequency and proportion for categorical variables. These summaries will be produced for both the FAS and the Injection analysis set. Generating inferential statistics is not planned.

Graded laboratory abnormalities will be defined using the NCI CTCAE grading scheme as defined in Section 12.3. Incidence of treatment-emergent laboratory abnormalities, defined as values that increase at least 1 toxicity grade from baseline at any time post baseline up to six months post-injection will be summarized. If baseline data are missing, then the latest value collected between biopsy and injection will be used as the baseline value. If baseline and pre-injection data are missing, then any graded abnormality, i.e., at least a Grade 1, will be considered treatment emergent.

Laboratory data summaries will be provided for both the FAS and the Injection analysis set. There are no plans to generate inferential statistics, except for variables concerning the rate of renal insufficiency progression. A paired t-test may be performed to assess the change in the rate of progression of renal insufficiency. Laboratory data will be provided in a data listing.

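### The treatment-emergent AE rule in section 14.7.2 has no worsening clause, so a biopsy-related AE that rises in grade after injection is, read literally, left out of the treatment-emergent summaries

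*Combined protocol and SAP*

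**What the plan says.** Section 14.7.2 gives one test for a treatment-emergent AE, its start date: "A treatment-emergent AE will be defined as any adverse event that begins on or after the date of enrollment up to 18 months post-injection". Treatment-emergent AEs are then tabulated by SOC and PT and by severity grade, for both the FAS and the Injection analysis set.

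Four other provisions fix what that test does:

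- **Enrollment is injection.** Section 10.1: "Note that a subject will be considered enrolled into the study at the time of injection".
- **Biopsy comes first.** The heading of section 11.2 places it 4 to 14 weeks before injection.
- **Biopsy AEs go on the AE page.** Section 13.3.1 sends an AE between biopsy and injection there if it is possibly or probably related to the biopsy or another protocol procedure. Section 13.3.3 has related AEs followed until they resolve, stabilize or return to baseline.
- **The same kidney is injected.** The synopsis says "all NKA injections are to be given into the kidney that was biopsied", and section 6.5.3 repeats it.

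Two other sections do deal with worsening. For laboratory abnormalities, 14.7.3 counts "values that increase at least 1 toxicity grade from baseline at any time post baseline". For conditions ongoing before study entry, which belong on the Medical History CRF, 13.1.1 says they "are not considered AE's unless the condition unexpectedly worsens during the study".

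**The concern.** The rule asks when an AE began and never whether it became worse. The first patient-level insult in this trial is a biopsy of the kidney that is later injected, so some patients may come to injection with a recorded, unresolved lesion in the target organ. If the injection aggravates that lesion, the harm happens after treatment, in an enrolled and injected patient who is in both analysis sets, yet the record carries a start date before enrollment.

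For example, a Grade 1 perirenal hematoma recorded after biopsy becomes Grade 3 on Day 5 after injection. Under the onset test it is not treatment-emergent and is absent from the SOC/PT and severity tables.

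The omission can only lower the tabulated count. It also falls in a sensitive place, since the synopsis names hemorrhage after the injection procedure as the greatest recognized risk.

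**Working it through.** The plan states no figure on this point, so there is none to reproduce. The check has two parts.

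**1. Does the exclusion follow from the text?**

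| Step | Source | Consequence |
|---|---|---|
| Onset must be on or after enrollment | 14.7.2 | Start date decides |
| Enrollment is at injection | 10.1 | The clock starts on Day 0 |
| Biopsy is 4 to 14 weeks earlier | 11.2 | Biopsy AEs start before the clock |
| Biopsy-related AEs go on the AE page | 13.3.1 | They carry that earlier start date |
| Grade increase in an open AE | No recording rule found | No new record or onset date is required |
| Worsening of prior conditions | 13.1.1 | Medical History items only, and only if unexpected |
| Laboratory worsening of at least 1 grade | 14.7.3 | Counted, but not carried over to clinical AEs |

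Read literally, the exclusion follows.

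**2. How many patients could it touch?** AV fistula is the lesion for which the plan gives both a frequency and a resolution figure.

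Inputs from the documents: section 13.4.1 states that "AV fistulas can be found in about 18% of patients that have undergone renal biopsy" and that more than 95% resolve within 2 years. Up to 30 patients are injected (14.1). Up to 7 Phase 1 patients (section 6) may return, possibly without a new biopsy, so newly biopsied patients number 30 − 7 = 23 to 30.

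Expected fistulas after biopsy: 23 × 0.18 = 4.1 to 30 × 0.18 = 5.4.

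Persistence to injection is not given. Assume exponential resolution with exactly 95% resolved at 104 weeks:

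- rate = −ln(0.05)/104 = 0.0288 per week
- present at 4 weeks: exp(−0.0288 × 4) = 0.89; at 14 weeks: exp(−0.0288 × 14) = 0.67
- share of biopsied patients: 0.18 × 0.89 = 0.160; 0.18 × 0.67 = 0.120
- patients: 23 × 0.120 = 2.8 to 30 × 0.160 = 4.8
- chance of at least one, 1 − (1 − p)^n: 0.95 (p = 0.120, n = 23) to 0.99 (p = 0.160, n = 30)

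These are patients who would carry a fistula at the time of injection if none were withdrawn. They are not missed events.

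A missed event also requires post-injection worsening, for which the documents give no rate. Expected number missed = n × 0.18 × persistence × worsening:

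- low: 23 × 0.18 × 0.10 × 0.05 = 0.02 (chance of any, 2%)
- full persistence, 25% worsening: 30 × 0.18 × 1 × 0.25 = 1.35 (chance of any, 75%)
- exponential persistence at 14 weeks, 10% worsening: 2.8 × 0.10 = 0.3
- exponential persistence at 4 weeks, 50% worsening: 4.8 × 0.50 = 2.4

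The range is therefore roughly 0 to 2 patients. One patient in 30 is 1/30 = 3.3 percentage points.

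**The case against.** **The investigator may stop such patients before injection.** Section 9 names excessive bleeding and AV fistula as examples of significant post-biopsy AEs that lead to discontinuation if the PI judges that they preclude safe injection. Section 12.5.1 has a comparable rule. Section 13.4.1 asks the PI to consider discontinuation when the pre-injection ultrasound shows a fistula. These rules stand and reduce the exposed group. All rest on judgement, so they do not empty it.

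**Section 13.1.1 may already cover worsening.** Study entry is not defined. If it means enrollment, an unexpected rise in grade could be called a new AE with a post-injection start. Section 13.3.1 also requires any AE occurring during or after injection to be recorded, and fresh bleeding from a new puncture could be entered as a new event. This shows ambiguity. It does not close the gap, because biopsy lesions sit on the AE page and not in Medical History, and because expected worsening would still be left out.

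**The event is not hidden.** All AEs are listed. A hemoglobin fall of at least one grade counts under 14.7.3. A serious worsening goes to SAE reporting, and a severe SAE related to NKA or to study procedures stops further injections pending DSMB review (13.6). This stands, and a reader should not infer that the harm would go unseen. One limit is that 13.2.1 asks for a relationship assessment per AE. If a non-serious worsening stays on the biopsy record, nothing prompts a fresh assessment against NKA, which is what sends an event to the DSMB under 13.5.

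**The primary safety outcome is not tied to this definition.** This also stands. A reader might infer that the primary outcome is itself under-counted. Section 14.3 speaks of procedure- and/or product-related AEs through 12 months after the initial injection and does not use the term treatment-emergent, so the documents do not support that inference.

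**The counts rest on assumptions.** This is true of persistence and worsening. In addition, 18% is the share in whom a fistula can be found, and 13.4.1 says fistulas should not be routinely pursued, so not every one will be detected or recorded as an AE.

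**Conclusion.** The gap is real but narrow. On its literal wording, 14.7.2 leaves out of the treatment-emergent SOC/PT and severity summaries a biopsy-related AE that was recorded before injection and rises in grade after it. The plan's own laboratory rule would count the analogous change.

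The number affected is unknown and probably small: roughly 0 to 2 of 30, assuming 23 to 30 newly biopsied patients, every fistula detected and recorded, no withdrawal by the PI, 10% to 100% persistence to injection, and 5% to 50% worsening afterwards. Detection, recording and withdrawal all push the fistula count down. Other biopsy lesions, such as hematoma, would add to it, and their persistence is not given. The 95% to 99% figure is the chance that someone carries a fistula to injection under the exponential assumption. It should not be read as the chance that an event is missed.

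The consequence is a possible under-count in summary tables, at about 3 percentage points per patient. It is worth correcting because the error runs in one direction and the correction is cheap.

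**What to change.** 1. **Section 14.7.2.** Define a treatment-emergent AE as one that begins on or after the first injection under this protocol, or that was present before that injection and afterwards increases by at least 1 CTCAE grade or becomes serious. This aligns clinical AEs with the laboratory rule in 14.7.3.
2. **Section 13.3.1 or the CRF instructions.** When an ongoing AE increases in grade after either injection, have the site open a new AE record with its own onset date, grade and relationship assessment. This also covers an AE that began after the first injection and worsens after the second, a case the plan does not address.

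The cost is about one sentence in each place, a few more AE records, and slightly higher reported AE counts. No clinical procedure changes.
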